### **6.3 Subject Screening**

SCI physicians at each site ([name] at Cleveland Clinic; [name] at Cleveland VA Medical Center; [name] at Kessler; [name] at MetroHealth Hospital) will screen patients at the beginning of the study to determine eligibility, either on-site or through a video screen for subjects who cannot reasonably make it to one of the sites. International Standards for Neurological Classification of SCI (ISNCSCI) will be used to confirm the diagnosis, the degree of completeness of injury (AIS A, B, C, or D), and zones of partial preservation below the level of injury. Strength or muscle power will be recorded using UEMS to identify the weaker upper limb. Physicians will quantify spasticity using the MAS and note any tightness and contractures. Complaints of neuropathic pain and autonomic dysreflexia will be noted. Medication usage will be screened and documented. Physicians will examine patients and exclude those with active pressure ulcers. Physicians will also determine whether patients had suffered an associated TBI at the time of SCI. A diagnosis of TBI will be made based on original radiographs and clinical records, as well as history and physical examination. Patients who are found to have had a Rancho Los Amigos Scale score of level V or below, and/or any MRI- or CT-evidence of focal cerebral cortex involvement or hydrocephalus from the time of injury, and/or history of (non-sedated) post traumatic amnesia lasting >48 hours, will be excluded. ISNCSCI, medical history and physical

Title: Improving Spinal Cord Injury Rehabilitation Interventions by Retraining the Brain

PI: [name]

Sub-site PI's: [name], [name], [name], [name], [name]

Protocol V 5.1 —2/3/2023

examination are considered part of the NINDS CDEs for SCI. Therapists will also conduct a screening to assess upper limb functionality before subjects are enrolled. This is done on-site before or after the physician screening, unless subjects are not within a reasonable distance to the Cleveland Clinic and a virtual visit is more appropriate.

### 6.3 Subject Enrollment

A subject is enrolled in the study after they have provided informed consent. The subject also has to meet all of the inclusion and none of the exclusion criteria determined by the site PI.

## 7. STUDY VISITS

### 7.1 Study Schedule

Figure 2 below provides a study flow diagram from the point of subject screening and consent through the final follow-up visit.

[figure not shown]

Fig.2

### 7.1a Schedule of Study Visits

Study Phase	Visit	Schedule
Screening/ Informed Consent	The screening/informed consent visit will occur with a single on-site visit or if necessary, an additional video screening before the on-site screening. After informed consent, screening functional tests will be performed.	1 on-site visit and a potential video screen
Baseline Rehab Functional and Neurophysiology Testing	Pre-Test #1 will involve functional tests and Neurophysiology (TMS, H-Reflex) tests. The visits will occur over 2 days and last 8-11 hours. Pre-Test #2 will involve functional tests and Neurophysiology (TMS, H-Reflex) tests. The visits will occur over 2 days and last 8-11 hours.	2 on-site visits (any day after informed consent/screening visit) 2 on-site visits (at least 3 weeks after Pre-test #1)
Rehab Phase	15 visits of rehab. During rehab visits subject will have SHAM or REAL tDCS administered. Each rehab session will last for 2 hours.	15 on-site visits. (5 times per week for 3 weeks)
Post-Rehab Functional and Neurophysiology Testing	Post-Test will involve functional tests and Neurophysiology (TMS, H-Reflex) tests. The visits will occur over 2 days and last 8-11 hours	2 on-site visits (within 1 week after the final rehab visit)

Title: Improving Spinal Cord Injury Rehabilitation Interventions by Retraining the Brain

PI: [name]

Sub-site PI's: [name], [name], [name], [name], [name]

Protocol V 5.1 —2/3/2023

3 Month Follow-up Testing	Follow-up will involve functional tests. This visit will last between 1-3 hours.	1 on-site visit, (OPTIONAL: +1 on-site visit) (3 months after the final rehab visit)
6 Month Follow-up testing (OPTIONAL)	Optional Neurophysiology testing (TMS, H-Reflex) Optional Follow-up will involve functional tests and Neurophysiology (TMS, H-Reflex)	2 on-site visits (6 months after the final rehab visit)
12 Month Follow-up testing (OPTIONAL)	Optional Follow-up will involve functional tests and Neurophysiology (TMS, H-Reflex)	2 on-site visits (12 months after the final rehab visit)

## 7.1b Schedule of Study Assessments

Schedule of Study Assessments															Post-Test	3-month Follow-Up	
Preliminary Screening	Informed consent/ Formal Evaluation	Rehabilitation															
		Pre-Test #1	Pre-Test #2	1	2	3	4	5	6	7	8	9	10	11	12	13	14
phone screening document	X																
Inclusion/Exclusion		X															
ASIA Classification		X															
Upper Extremity Motor Score(UEMS)		X															
MRC Muscle Strength Scale		X															
Spinal Cord Independence Measure(SCIM)		X	X													X	X
Canadian Occupational Performance Measure (COPM)		X	X													X	X
GRASSP		X	X													X	X
Neurogenic Bladder Symptom Score (NBSS)		X	X													X	X
Modified Ashworth Scale (MAS)		X	X													X	X
Capabilities of Upper Extremity Test (CUE-T)		X	X													X	X
Transcranial Magnetic Stimulation (TMS) Neurophysiology Tests		X	X													X	X
H-Reflex		X	X													X	X
TMS Adverse Effects Questionnaire		X	X													X	X
vital signs(blood pressure, heart rate, respirations, blood oxygen saturation)		X	X	X	X	X	X	X	X	X	X	X	X	X	X	X	X
tDCS Adverse Effects' Questionnaire				X	X	X	X	X	X	X	X	X	X	X	X	X	X

Fig.3

## 7.2 Baseline TMS and Functional Testing

Patients found to be eligible after screening will be tested on pre-test 1 and pre-test 2 (fig. 2). Both pre-test 1 and pre-test 2 will be conducted over 2 days lasting 8-11 hours (1 day functional testing, 1 day neurophysiology testing). They will be asked to continue with their typical routine and activities during what will be called the baseline control phase, lasting for 3 weeks. Patients will be asked specifically to refrain from participating in new training regimens involving the paretic upper limbs. During the Baseline Control Phase subject will participate in 2 Pre-testing visits. During each pre-test visit subject will undergo functional tests and Neurophysiology tests as seen in figure 3. There will be a 3 week break period between each pre-test visit (pre-test visits 2 should be at least 14 days after pre-test visits 1).

## 7.3 Rehabilitation with tDCS

Each subject with SCI will perform rehabilitation while receiving tDCS (randomly assigned active or sham stimulation) for 15 total visits.

Title: Improving Spinal Cord Injury Rehabilitation Interventions by Retraining the Brain

PI: [name]

Sub-site PI's: [name], [name], [name], [name], [name]

Protocol V 5.1 —2/3/2023

### **7.3a Rehabilitation**

Patients in both groups will receive 15 sessions of rehabilitation delivered for 2 hours a day, 5 days a week, for 3 weeks. Rehabilitation will be prescribed by site physical therapists: the PI [name] at Cleveland Clinic; [name] at Kessler; [name] at Cleveland VA Medical Center; and [name] at MetroHealth Hospital. Rehabilitation will be based on the principle of massed practice [17, 66, 67]. Massed practice involves intensively engaging the paretic upper limbs in 10-15 tasks. Massed practice has shown promise at reducing the weakness of the upper limbs in our recent study and studies by other groups [17, 61, 66, 67].

Training of the weaker upper limb will be emphasized with massed practice. Training of the weaker upper limb is more functionally relevant than training of the stronger one. In addition, training of the weaker upper limb will also maximize the potential of restoring function with tDCS. tDCS will be delivered using the typical uni-hemispheric montage, i.e., targeting the hemisphere contralateral to the weaker limb. The weaker upper limb will be identified based on patient report and UEMS collected at screening. About 80% of the tasks will engage the weaker upper limb, while remaining tasks will engage both limbs.

Tasks will be chosen based on the patient's preference and priority for achieving functional independence and will be designed so as to maximize the transfer to performance of real-world activities. Similar to practices commonly used in rehabilitation clinics, tasks will primarily engage muscles innervated below the level of injury (C6-T1). Engagement of the weak triceps (C7) will be especially emphasized, for instance, through activities like rising from a chair while pushing on armrests, or reaching for different targets positioned on a tabletop. Return of triceps strength is functionally relevant because triceps is critical for performing transfers to and from the wheelchair/surfaces and reducing caregiver assistance.

Each task will be performed 10 times and will be repeated if deemed necessary. Performance metrics like speed, accuracy, number of trials completed, etc., will be recorded and tracked. Feedback will be provided. Tasks will be made more (or less) challenging as patients recover movement abilities [76, 79]. Patients will also be asked to practice the tasks at home for 30 min a day, 5 days a week, for 3 weeks. Adherence to home exercises will be monitored using a home-exercise log that will be shared with investigators at every training session.

### **7.3b tDCS**

Transcranial Direct Current Stimulation (tDCS) will be delivered using a 9-V battery-operated device (Soterix Medical, New York, NY). Surface electrodes will be placed inside saline-soaked sponge inserts (5x7 cm^2) and applied to different regions on the scalp. The anodal electrode will be applied over the primary motor cortex, contralateral to the weaker upper limb. The center of the electrode will be positioned at a site evoking the largest muscle potentials in weak triceps using TMS (details follow). Location of the rectangular electrode (four corners and center) will be marked using stereotactic navigation. An overlap of the electrode locations will be generated for the 15 sessions to establish reproducibility. The cathodal electrode will be applied over the opposite supra-orbital area.

Current will be delivered at a dose of 2mA. Currents will be delivered for the first 30 minutes of the first hour of rehabilitation and the first 30 minutes of the second hour of rehabilitation for each rehab session. Sham tDCS

Title: Improving Spinal Cord Injury Rehabilitation Interventions by Retraining the Brain

PI: [name]

Sub-site PI's: [name], [name], [name], [name], [name]

Protocol V 5.1 —2/3/2023

will be delivered using the same application, but currents will be ramped up slowly at the beginning and ramped down slowly at the end. This sham technique facilitates blinding of the subject.

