[name] has over a decade of experience in delivering TMS and training others in the delivery of TMS. In this study we will collaborate with other experienced researchers in the field of TMS; [name] (Kessler Foundation), [name] (MetroHealth Hospital) and Drs. [name] and [name] (Cleveland VA). Drs. [name] and [name] were previous colleagues and collaborators at the Cleveland Clinic Foundation prior to [name] transition to Kessler Foundation. At the Cleveland Clinic, Drs. [name] and [name] led and developed multiple protocols for TMS as is evident by their co-published articles [8-15]. Therefore, both Drs. [name] and [name] are well trained in identical methodology in TMS protocols and possess the same equipment to deliver TMS. Drs. [name] and [name] are experts in TMS as well and have performed TMS studies with [name] for a number of years [1-3, 8, 11, 12, 16-22]. Therefore, the prior success of collaborations between Drs. [name], [name], [name] and [name] for TMS studies indicates that standardization of TMS methodology across sites would not be difficult. All study staff will be trained by Drs. [name], [name], [name] and [name] at each site, and standard operating procedures for TMS will be developed and distributed by [name] and [name] [name] upon site visits within the first 4 months of the clinical trial in year 1. [name] was a previous student of [name] at the Cleveland Clinic, therefore the methodology of delivering TMS will be easily translated for this current trial. [name] and his team at MetroHealth Hospital will be trained during the first quarter of the fourth year (September 2021-November 2021).

- *Rehabilitation*

[name] has worked with SCI patients for upper limb rehabilitation for over 4 years through her recent DoD-funded study [1-3]. Sample rehabilitation tasks from the previous pilot study will be dispersed between sites to aide in customization of therapy tasks for each patient, between physical therapists ([name] at the Cleveland Clinic, [name] at Kessler Foundation/Kessler Institute for Rehabilitation, [name] at MetroHealth Hospital and [name] at the Cleveland VA Medical Center). In addition, study staff at each location involved in therapy will be trained by [name] on delivering rehabilitation based on massed-practice.

- *Transcranial Direct Current Stimulation*

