[name] has had over a decade of experience in using transcranial direct current stimulation (tDCS) to promote restoration of functional outcomes in applications ranging from vision to motor ability. With her experience, [name] has been able to optimize a dosage schedule for tDCS delivery for the proposed clinical trial using her previous pilot study. Therefore, since all the same equipment exists at all locations, during the first fiscal year site visit in month 4, [name] will advise [name], [name] and [name] along with their respective research personnel how to properly apply the tDCS stimulation during rehabilitation.

Title: Improving Spinal Cord Injury Rehabilitation Interventions by Retraining the Brain

PI: [name]

Sub-site PI's: [name], [name], [name], [name], [name]

Protocol V 5.1 —2/3/2023

It would be important to ensure consistency of dosing or treatment fidelity in application of rehabilitation. Safeguards are planned to ensure that all patients participating at all study sites receive the same dose of massed-practice rehabilitation for same length of time, with a similar ratio between tasks practiced with the weaker upper limb and those practiced with the stronger upper limb. Therefore, therapists at all sites, including the PI [name] at the Cleveland Clinic, [name] at the Cleveland VA medical center and [name] at the Kessler Foundation/Kessler Institute for Rehabilitation will participate in Skype phone/video calls before starting treatment for any patient in the first year of the study. These meetings will allow every therapist to become more comfortable with dosage and frequency required for the proposed protocol. Therapists will have one additional meeting in the middle of the training regimen (session 7 or 8 out of 15) to ensure continued treatment fidelity. In years 2-4, therapists will have similar meetings for every other patient to ensure that even over several years, consistency of fidelity of rehabilitation delivery is maintained. [name] at MetroHealth Hospital will be trained on administering tDCS by [name] and [name] during the first quarter of the fourth year (September 2021-November 2021).

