### **2.2 Soterix tDCS Principle of Operation**

For the specific steps on how to operate the Soterix Medical DC Stimulator, refer to the device manual.

Transcranial Direct Current Stimulation is treatment that utilizes electrode pads placed at opposing points on the scalp and a direct current stimulator to deliver electrical energy which transfer from the anode, across the scalp and skull, to the targeted location in the brain and then to the cathode placed at a different location on the scalp.

For the proposed indication, the aim is to deliver continuous bilateral transcranial direct current stimulation, directing the anode to the contralateral motor cortex of the more affected upper limb. The cathode will be placed on the ipsilateral orbit of the more affected upper limb. This will allow the current to flow from the motor hotspot (of the weaker muscle in the more affected upper limb) to its contralateral orbit.

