#### 6.1a General Inclusion Criteria

Patients with incomplete (having sparing to muscles in the upper extremities below the level of injury) C1-C8 SCI; age  $\geq 18$  years;  $\geq 1$  year time post injury (to avoid confounding effect of cervical root recovery [77]) will be enrolled. On the more affected side, patients will be required to have sparing of either the biceps or the triceps muscle, defined as  $\geq 3$ -muscle power grade on the MRC scale. They will also be required to show weakness of the muscle antagonist to the spared muscle i.e. triceps in case of spared biceps, or biceps in case of spared triceps on the affected side. Weakness will be defined as a MRC grade of 1-3, and a clinically detectable difference in power compared to the power of the spared muscle, i.e.,  $\geq 1$  muscle grade lower on the MRC scale [63, 64]. Criteria requiring sparing of one muscle and the weakness of the antagonist muscle are meant to create a homogeneous sample for the study of neurophysiology using TMS in Aim 2. These criteria will not be limiting for subject recruitment, as evident from the successful completion of our recent pilot work, because patients with cervical SCI either commonly show sparing of biceps (C5) and weakness of triceps muscles (C7), or this order of weakness is reversed in patients with central cord syndrome [60, 61]. On the contrary, these criteria will allow inclusion of even more-impaired individuals, who may not have “active hand function” as required by typical SCI studies [66, 68] and an ongoing study (NCT02611375).

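### For patients whose weak muscle is the biceps, the anode-centre rule in section 7.3b conflicts with the target described in section 2.2

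*Combined protocol and SAP*

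**What the plan says.** Four parts of the combined protocol and SAP bear on this.

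- **Section 6.1a (inclusion).** One of biceps or triceps on the more affected side must be spared (MRC grade 3 or more) and its antagonist must be weak (grade 1-3, and at least one grade below the spared muscle). The weak muscle may be "triceps in case of spared biceps, or biceps in case of spared triceps on the affected side". The second pattern is foreseen: the section says that "this order of weakness is reversed in patients with central cord syndrome".
- **Section 7.3b (tDCS procedure).** The anode goes over the primary motor cortex contralateral to the weaker limb, and its centre is "positioned at a site evoking the largest muscle potentials in weak triceps using TMS (details follow". No rule is given for a patient whose triceps is the spared muscle. The section adds: "Location of the rectangular electrode (four corners and center) will be marked using stereotactic navigation".
- **Section 2.2 (principle of operation).** Current is described as flowing from the "motor hotspot (of the weaker muscle in the more affected upper limb" to the orbit on the other side. This identifies the muscle by its role, not by name.
- **Section 1.4 (site information).** For TMS, "standard operating procedures for TMS will be developed and distributed" to the sites, and study personnel are to be advised "how to properly apply the tDCS stimulation during rehabilitation".

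**The concern.** The anode centre is part of the intervention under test. The protocol treats it as such: it locates the site by TMS, marks it by navigation and checks reproducibility over the 15 sessions. The rationale in sections 3.4 and 4.2 rests on shifting representation from spared to weak muscles, so which muscle defines the centre matters to the trial's own logic.

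For a weak-biceps patient, a site that follows 7.3b literally would centre the anode on the site of the spared muscle. A site that follows 2.2 would centre it on the site of the weak one. Four sites deliver the intervention, and two careful readers could place the electrode differently in patients whom the eligibility criteria expressly expect.

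**Working it through.** The check is textual and rests on no sample size or power figure.

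**Step 1. Can a weak-biceps patient also have a weak triceps in the protocol's sense?** If so, 7.3b could still apply as written. Let B and T be the MRC grades of biceps and triceps on the more affected side. Under 6.1a, a weak-biceps patient satisfies:

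- T ≥ 3 (triceps spared);
- 1 ≤ B ≤ 3 (biceps weak);
- T − B ≥ 1 (detectable difference).

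With grades 0 to 5, the admissible pairs (B, T) are (1,3), (1,4), (1,5), (2,3), (2,4), (2,5), (3,4) and (3,5): eight in all. For the triceps to count as weak under the same definition, it would need 1 ≤ T ≤ 3 and B − T ≥ 1. The second condition contradicts T − B ≥ 1, so none of the eight pairs qualifies. In (1,3) and (2,3) the triceps grade lies within 1-3, but the triceps is still the stronger muscle of the pair.

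**Step 2. Compare the two placement texts for each pattern.**

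| Pattern admitted by 6.1a | Muscle in 2.2 (the weaker one) | Muscle in 7.3b (weak triceps) | Agree? |
|---|---|---|---|
| Weak triceps, spared biceps | triceps | triceps | yes |
| Weak biceps, spared triceps | biceps | triceps, or none if the words are taken not to apply | no |

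**Step 3. What is left under each reading of the second row.** If 7.3b means the triceps whatever its grade, it contradicts 2.2. If 7.3b is taken as silent because the patient has no weak triceps, the operative procedure has a gap and only the general description in 2.2 remains.

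**Step 4. Do the promised details resolve it?** The rest of 7.3b gives the cathode position, current, timing and sham method. Sections 7.4 to 7.6 cover post-testing, follow-up and the healthy-control visit. None gives a rule for choosing the muscle. Figures and a few pages are not visible in the available text.

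**Step 5. What is not in conflict, and one neighbouring mismatch.** Sections 2.2 and 7.3b agree on the hemisphere, and their cathode descriptions are compatible. However, 2.2 calls the stimulation *bilateral*, while 7.3a describes a *uni-hemispheric* montage. These descriptions also need to be reconciled.

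**Step 6. Aim 2.** Hyp. 2 in section 5.4 names the triceps (C7) as weak and the biceps (C5) as spared. Sections 5.1, 5.2 (weak map over strong map) and 9.4 define the measures by role. The analysis text therefore already accommodates weak-biceps patients, and the wording of Hyp. 2 is an editorial matter.

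**The case against.** The case for leaving the text alone has several parts.

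- **Triceps may be shorthand for the usual case.** Section 5.1 offers the triceps as an example of a weak muscle, and 7.3b may have been written with the same patient in mind. That is plausible. But 5.1 marks the triceps as an example and 7.3b does not, so the mismatch remains, although a short clarification would remove it.
- **Section 2.2 is a weak counter-text.** It describes a principle, refers to the device manual for operating steps, and is loose about the montage. Section 7.3b is the operative procedure. This is fair, but giving 7.3b precedence is exactly what leads to the spared muscle's site in weak-biceps patients.
- **Other documents may settle it.** The anode site is found by TMS, and section 1.4 provides for written TMS procedures as well as tDCS training. These are natural places for the rule. This stands: a reader might infer that the protocol was the only written reference shared by the sites, and section 1.4 does not support that. The cross-site therapist calls in 1.4 show further contact, though they concern fidelity of rehabilitation.
- **Placement is recorded.** The navigation marks allow actual placement to be described afterwards.
- **It is late.** Section 1.4 puts November-December 2018 at about three months into the study and enrolment at about six months, hence around early 2019. Section 1.3 allows five years from first enrolment. Version 5.1 is dated 2/3/2023, so on the planned timeline about four of the five years had passed. Actual enrolment is not stated, and a clarification might reach few further patients.

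These points limit the likely consequence. They do not make the sections agree.

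**Conclusion.** The inconsistency is real and is confined to patients with a weak biceps and a spared triceps. For them, 7.3b either names a different muscle from 2.2 or leaves only the general description in 2.2. It should be corrected because it concerns a stated rule of the tested intervention and costs very little to put right.

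Its size cannot be given. The documents state neither the share of weak-biceps patients nor the distance between the biceps and triceps sites, and any figure would only restate an assumption. Confidence is high in the textual mismatch, not in any consequence for the results.

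Stronger conclusions that a reader might draw are not supported:

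- **That the sites placed electrodes differently.** The procedures and training that would show this are not in the documents.
- **That the protocol gives these patients no target at all.** Section 2.2 still describes one in general terms.
- **That the comparison is biased or has lost power.** Nothing in the documents ties the ambiguity to one arm's allocation or allows an effect to be calculated.
- **That Aim 2 would be scored wrongly in these patients.** Sections 5.1, 5.2 and 9.4 define its measures by weak and spared or strong muscle.

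**What to change.** - The investigators should reconcile sections 2.2, 6.1a and 7.3b so that 7.3b states what applies when the triceps is not the weak muscle. If the TMS procedures already contain the rule, 7.3b can cite them in place of the unfulfilled promise of details. Which site to use is for the investigators; none is proposed here.
- At the same time, reconcile *bilateral* in 2.2 with *uni-hemispheric* in 7.3a.
- Report the number of patients with each weakness pattern by arm. The muscle grades needed to apply 6.1a are recorded at screening, so no new data are required.
- As an editorial note only, word Hyp. 2 by weak and spared muscle to match section 9.4.

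The cost is about one sentence in 7.3b sent to the four sites, two small wording changes and one descriptive table row. Sample size, visits and assessments do not change. If enrolment has finished, the count by pattern and arm can still be reported.
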